#### *Safety Monitoring*

The following procedures/evaluations will be conducted as part of the study safety assessment:

- **Medical examination** at enrollment and day 15 of follow-up: assessment of height, weight, MUAC, vital signs (i.e., temperature, pulse, respiration rate), organ systems, breathing, hydration status, fontanelles, and skin irritation/rashes.
- **Counseling procedures** that need to be adhered to during study participation.
- **Assessment of study intervention adherence** via measurement of residual solution will be performed on each bottle (numbered 1–21).
- **Assessment of adverse events** including solicited AEs (i.e., vomiting, diarrhea, fever, constipation, irritability, allergic reactions, etc.) and unsolicited AEs by study nurse initially in person, and subsequently by phone (days 4, 7, 14, 21), and review of any AEs/SAEs by study clinician.
- **Assessment of child weight** by the RA, who will weigh the child at interim visits on day 7 and 14.

To screen children for recent illness or chronic illness (e.g. HIV, hepatitis, etc.), medical charts created as part of regular medical care will be reviewed, as available. Confidentiality of medical records will be protected.

#### *Adverse Events and Serious Adverse Events*

All participants will be monitored closely for adverse events during the study at five time points by the study nurse. The nurse will do these assessments 60 minutes after the first administration (in person) and via phone questionnaire on days 4, 7, 14, and 21. All clinical personnel involved in the study will be trained in identifying adverse events and all participants will be educated regarding symptoms that require urgent medical attention. Any adverse events will be managed by the appropriate clinic site, and if necessary, hospitalization. The costs of care directly attributable to participation in the study

will be borne by the study sponsor. The clinical site involved in this study is a Provincial Hospital, which can provide emergency care if necessary.

#### *Definition of Adverse Event (AE)*

An adverse event (AE) is any untoward medical occurrence in a participant after administration of the study product and that does not necessarily have a causal relationship with the study product. An AE can therefore be any unfavorable and unintended signs (including abnormal laboratory findings), symptoms, physical examinations, or disease temporally associated with the use of the study product, whether related to the study product or not. This definition includes exacerbations of pre-existing conditions. Stable pre-existing conditions that do not change in nature or severity during the study are not considered AEs; however, these should be reported as part of the medical history.

**Solicited AEs** are pre-specified adverse events that are actively monitored by study staff during the full 21 days of follow-up. Personal communication with the study product manufacturer indicated that no adverse events have been found to be associated with the AA-ORS in adult studies or in the small study (n=5) featuring children with short bowel syndrome.

For this study, solicited AEs will be assessed by study nurse 30 minutes after the first administration (in person), and then by phone on days 4, 7, 14, and 21.

The following specific solicited adverse events will be monitored for this trial:

- *Vomiting.*
- *Diarrhea.*
- *Fever.*
- *Constipation.*
- *Lethargy.*
- *Irritability/restlessness.*
- *Allergic reactions:* sudden swelling of the face or throat, itching, and rash.
- *Other reactions:* fits (convulsions/seizures); gas, abdominal cramps, or stomach pain; weight loss.

Changes in the severity of an AE (e.g., diarrhea) will be documented to allow an assessment of the duration of the event at each level of severity to be performed. AEs characterized as intermittent require documentation of onset and duration of each episode.

**Stopping rule:** RAs will weigh children in the household on a weekly basis (end of weeks 1 and 2). If a child loses more than 5% of his or her body weight from that measured at enrollment, he/she will be withdrawn from the study. The study team will refer the withdrawn child and caregiver to his or her primary health care provider or CGH, as appropriate. In addition, there will be a review of the first 10 enrolled breastfeeding participants by the investigators and ISM. If two of the first 10 participants who are breastfeeding at enrollment stop breastfeeding during the 2-week course of the study, the study will halt the enrollment of children who are currently breastfeeding. If there is evidence of a negative impact on participants' breastfeeding, PATH REC will be notified.

**Unsolicited AEs** are any significant events not specified as a solicited AE by study personnel and can be reported spontaneously by the participant, observed by the study personnel during study visits, or identified during review of medical records or source documents.

Any medical condition that is present at the time that the participant is screened will be considered as baseline and not reported as an AE. However, if the study participant's condition deteriorates at any time during the study, it will be recorded as an AE.

Changes in the severity of an AE will be documented to allow an assessment of the duration of the event at each level of severity to be performed. AEs characterized as intermittent require documentation of onset and duration of each episode.

#### *Serious Adverse Event (SAE)*

A serious adverse event (SAE) is any adverse event that results in any of the following outcomes:

1. Death.
2. Is life-threatening (life-threatening means that the study participant was, in the opinion of the site PI or sponsor, at risk of death at the time of the event; it does not refer to an event that hypothetically might have caused death if it were more severe).
3. Requires inpatient hospitalization or prolongation of existing hospitalization.
4. Results in persistent or significant incapacity or substantial disruption of the ability to conduct normal life functions.
5. Is an important medical event that may not result in one of the above outcomes but may jeopardize the health of the study participant or require medical or surgical intervention to prevent one of the outcomes listed in the above definition of serious adverse event.

#### *Suspected Unexpected Serious Adverse Reactions (SUSARs)*

A suspected unexpected serious adverse reaction (SUSAR) is a serious adverse reaction that is not identified in practice, severity, or frequency by the reference safety information. A SUSAR must meet the criteria for an SAE and also be determined to be related to the study product.

#### *Reporting Period and Parameter*

Safety events are reported from the time of the first study product administration through completion of the study 21 days later. Specifically, solicited AEs will be collected up to 30 minutes after the first administration and on days 4, 7, 14, and 21. Both solicited and unsolicited AEs and SAEs will be assessed through 7 days after the end of the study product dosing. The final AE and SAE assessment will be done via a phone call on day 21 (or within 3 days thereafter):

1. The caregiver will be contacted via telephone and identity confirmed.
2. Study nurse will ask about any medical event that would constitute an AE or SAE since the last visit.
3. If an AE or SAE is reported, the nurse should record it on the appropriate CRF and consult the study clinician, who will notify the entities who require notification. The nurse will refer the participant for treatment, if warranted.

After recording the information, the participant will be discharged from the study.

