Upon return to the clinic ( $\geq 1$  week post screening visit) the RA will review the consent form with the parent or legally acceptable representative and answer any questions. The caregiver will be asked if they are still interested in continuing with participation in the study; if they agree, then the RA will complete the informed consent process and obtain their written signature on the consent form.

Once the consent form is signed and a copy has been given to the participant, the study nurse or clinician will conduct a medical examination, and a trained phlebotomist will draw blood from the child and collect a bloodspot on filter paper (see "Blood specimen collection and processing"). The RA will then proceed with the enrollment questionnaire and direct observation of the oral solution. For all children who join the study and are still breastfeeding, the enrollment questionnaire will include questions to establish a baseline breastfeeding rate (how many times a day). After direct observation of dosing with the solution, an RA will complete an IDI with the caregiver.

Training of caregivers

Caregivers will receive one 237-ml bottle of AA-ORS or placebo at enrollment along with a small cup and spoon to aid administration. The RA will train the caregiver to give the solution to their child and show them how to properly seal the bottle (containing unused solution) following solution provision (Appendix 6). The caregiver will administer the solution to their child in a private room in the clinic, under direct observation by an RA for 3 hours or until the solution has been finished, whichever comes first. Breastfeeding and solid feeding is permitted whenever desired during the 3-hour period.

Direct observation:

The goal of DOs is to directly witness the administration of AA-ORS or placebo solution and instruct caregivers to properly reseal bottles with unused solution. Target observations during the DOs include:

- Perceived palatability of study product by children.
- Perceived acceptable volume of study product by children.
- Ease of administration of study product by caregivers to their child.

Interim visits:

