#### *Blood Specimen Collection and Processing*

Between 1 and 1.5 ml venous blood will be collected from each child twice—at enrollment and at the post-dosing visit, 15 days after onset of the intervention. A trained phlebotomist will perform venipuncture using a technique appropriate for children who are younger than 2 years old, and a small drop of blood will be blotted from the insertion site and dried on filter paper. Blood samples will be centrifuged into plasma and/or serum within 30 minutes of collection and stored in cryo tubes at less than  $-20^{\circ}\text{C}$  until they can be analyzed. Commercial enzyme-linked immunosorbent assays (ELISA) and a Quansys Biosciences Q-Plex™ panel will be used to quantify plasma/serum micronutrients, EED markers (intestinal fatty acid-binding protein [I-FABP], soluble CD14 [sCD14], glucagon-like peptide 2 [GLP-2], insulin-like growth factor 1 [IGF-1], and fibroblast growth factor 21 [FGF21]), and systemic inflammation (alpha-1-acid glycoprotein [AGP] and C-reactive protein [CRP]). Mass-spectroscopy will be used to evaluate metabolic markers from dried bloodspot (e.g., acylcarnitine profile) to ascertain whether there is a tendency for child metabolism to switch to an oxidative state when supplementing a subset of essential amino acids. Detail provided in Table 5, below.

**Table 5.** Plasma/serum biomarkers assessed in SAFE at enrollment and post-dosing visit.

Biomarker	Assay name	Company	μl of plasma required (per well)
I-FABP	Human I-FABP ELISA	Hycult	25
GLP-2	GLP-2 ELISA Kit	ALPCO	25
IGF-1	Human IGF-I Quantikine ELISA Kit	R&D Systems	20
sCD14	Human CD14 Quantikine ELISA Kit	R&D Systems	10
FGF21	Human FGF-21 Quantikine ELISA Kit	R&D Systems	50
AGP	Q-Plex™ Human Micronutrient (7-Plex)	Quansys	10
CRP			
Ferritin			
sTfR			
RBP4			
Thyroglobulin			
HRP2			
Acylcarnitine	Acylcarnitine profile analysis	Mass spectrometry	40 (80 μl whole blood)
Total			320

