#### *Causality of Adverse Event*

The study investigator/s will determine the causal relationship between the study product and the AE. The causality assessment is made on the basis of the available information at the time of reporting and can be subsequently changed according to follow-up information. Determining of causality is based on clinical judgment and should take into considerations the following factors:

- Is there a temporal (time-based) relationship between the event and administration of the study product?
- Is there a plausible biological mechanism for the study product to cause the AE?
- Is there a possible alternative etiology for the AE such as concurrent illness or concomitant medications?
- Are there previous reports of similar AEs associated with the study product?

For this study, the investigator/s must classify the causality of the AE according to the categories defined below:

**Related:** There is a reasonable possibility that the product caused the event. “Reasonable possibility” means that there is evidence to suggest a causal relationship between the study product and the AE.

**Not Related:** There is not a reasonable possibility that the administration of the study product caused the event.

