### i. Risks to research study participants/groups

#### *Risk Considerations*

The proposed study is expected to be of minimal risk as the study AA-ORS is a medical food product regulated by the US FDA. As a result, we do not anticipate any adverse events for this study related to the administration of AA-ORS, but we will include a control arm in order to better assess the safety of this product in children with mild-moderate stunting. Children with mild to moderate stunting are at increased risk for morbidity and mortality, so we anticipate that participants may report diarrhea or respiratory infections at high rates, regardless of receipt of active AA-ORS or placebo. While there is mounting evidence that microbiome immaturity contributes to growth deficits in LRS, any changes to the microbiome composition and diversity from provision of AA-ORS are likely to be transient, based upon previous observations among infants and children provided probiotic-supplemented formula or ready-to-use supplementary food (43, 44).

This study involves blood specimen collection. The collection of these samples involves venipuncture, which may cause discomfort, pain, introduction of infection, bleeding, fainting, or bruising. Precautions will be taken to avoid introduction of infection by disinfecting the site of venipuncture and using sterile equipment. The risk of bleeding and bruising will be minimized by immediate application of pressure after venipuncture. The child will be restrained appropriately by the caregiver to prevent kicking of the phlebotomist. A thorough description of potential risk considerations and mitigation strategies is outlined in Table 7.

**Table 7.** Known risks and mitigation strategies for SAFE study participants.

Potential risk to participant	Concern	Study design feature intended to minimize risk	Rationale for the necessity of exposing participants to risk

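### Adverse event recording opens at the first dose, but the enrollment blood draw comes before it, so immediate complications of half the planned draws are not AEs or SAEs as the protocol defines them

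*Combined protocol and SAP*

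**What the plan says.** **Window and definitions (section C.x).** Reporting Period and Parameter sets the window: "Safety events are reported from the time of the first study product administration through completion of the study 21 days later". Definition of Adverse Event (AE) matches it, since an AE is "any untoward medical occurrence in a participant after administration of the study product". The SAE definition builds on this: "A serious adverse event (SAE) is any adverse event that results in any of the following outcomes". The 24-hour duty under Reporting of SAEs and SUSARs applies to SAEs as the protocol defines them.

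**Order of the enrollment visit (Study Procedures).** After signed consent and a medical examination, "a trained phlebotomist will draw blood from the child and collect a bloodspot on filter paper". Only then: "The RA will then proceed with the enrollment questionnaire and direct observation of the oral solution". Key Activities, items 2 to 4, gives a consistent order: consent and randomisation, blood sample, then product.

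**Two draws per child (Blood Specimen Collection and Processing).** Blood is taken "at enrollment and at the post-dosing visit, 15 days after onset of the intervention".

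**Recognised harms.** Risk Considerations says of venipuncture that it is a procedure "which may cause discomfort, pain, introduction of infection, bleeding, fainting, or bruising". Table 7 lists blood draw as a risk as well.

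**Attribution.** Causality of Adverse Event has two categories, both about the product. The negative one reads: "There is not a reasonable possibility that the administration of the study product caused the event".

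**The concern.** Venipuncture is the invasive study procedure, it is done in children aged 12 to 24 months, and the protocol names its harms. A plan that recognises these harms should be able to say how often they occurred. By definition, bleeding or fainting at the enrollment draw precedes the first dose, so it does not meet the AE definition and does not trigger the SAE duty.

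The children most affected could also drop out of the tables. Key Activities randomises before the draw, one exclusion criterion is inability to give the blood sample, and the intention-to-treat population requires at least one dose. A child whose draw goes badly and who is then not dosed would be randomised but appear in no safety table.

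At stake is what the DSMB, the ethics committees and the regulator learn about the safety of the study procedure. The estimate of product safety is not at stake.

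**Working it through.** **1. Does the draw fall outside the window?** The order is consent, examination, draw, questionnaire, first dose. The window opens at first dose. An immediate complication of the enrollment draw therefore comes before the window. One that first shows itself after the dose, such as a later infection, falls inside it.

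**2. Does another rule pick up the interval?**

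| Section | What it provides | Does it cover the draw-to-dose interval? |
|---|---|---|
| Definition of AE, text on unsolicited AEs | Baseline is fixed at screening; worsening at any time in the study is an AE | It conflicts with the post-dose definition, but concerns conditions already present. A new draw complication is neither baseline nor, by definition, an AE |
| Table 4 | SAE reporting and an AE check are marked on the enrollment day | It works by day, so it does not say whether pre-dose events count |
| Clinical information (D.iii) | AEs assessed at the screening, enrollment and day 15 examinations | Screening precedes any dose, so this contradicts the AE definition. The enrollment examination precedes the draw and cannot detect its complications |
| Safety Oversight | DSMB assesses the safety of study procedures | A remit only; no form or time point collects the events |
| First AE check | 30 minutes after the dose in Table 4, Definition of AE and Reporting Period; 60 minutes in Adverse Events and Serious Adverse Events | Timed from the dose in every version |

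The sections disagree about when recording starts, and none states that events between draw and dose are to be recorded.

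**3. How many draws?** Inputs are 66 children (section C.v), two draws each, and dropout of at most 10% (Sampling Strategy).

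- Planned draws: 66 × 2 = 132. Pre-dose: 66. Share: 66/132 = 50%.
- With 10% dropout before the second draw: 66 × 0.90 = 59.4. Share: 66/(66 + 59.4) = 66/125.4 = 52.6%.

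**4. How many events?** The documents give no complication rate, so the rates p below are assumptions chosen to show a range. Expected pre-dose complications = 66p. Chance of at least one = 1 − (1 − p)^66.

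| Assumed p per draw | Expected, 66p | At least one |
|---|---|---|
| 1% | 0.66 | 1 − 0.99^66 = 48.5% |
| 2% | 1.32 | 1 − 0.98^66 = 73.6% |
| 5% | 3.30 | 1 − 0.95^66 = 96.6% |

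**5. Is the Fisher comparison affected?** A pre-dose event cannot be caused by the product, and both arms undergo the same draws. Leaving such events out of the arm comparison does not bias it.

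**The case against.** The best defence is that this is a product-safety trial, for which a window starting at first dose is coherent, and that children are not left unprotected. A study nurse is on site, the child is seen in person after the dose on the day of the enrollment draw, and the sponsor covers study-related injury. All of that stands. It concerns care and the product comparison, and does not settle whether the event is recorded.

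Three stronger readings are tempting, and the documents do not support them.

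- *A reader might infer that enrollment-draw complications are shut out of every safety report.* The baseline rule, the Table 4 mark and the Clinical information text lean towards earlier capture. Unsolicited AEs include events that staff observe at study visits. Sponsor Reporting to Regulatory Agency also requires reporting of information that could affect trial conduct. Staff might well report a serious pre-dose event. What can be said is that it is not an AE or SAE under the stated definition.
- *A reader might infer that the same harms are counted at day 15 and inflate the product AE totals.* They are eligible, but bleeding, bruising and fainting are not on the solicited list, and unsolicited AEs are limited to significant events. The Post-dosing visit text puts the examination before the draw, and the next scheduled AE contact is the day 21 call. That they would be counted is not shown.
- *A reader might infer that no form can mark an event as procedural.* The case report forms are in Appendix 2, which is not among the documents. Only the causality categories in the protocol text can be judged.

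**Conclusion.** The gap is real but limited. Immediate complications of 66 of 132 planned draws (50%, or 52.6% with 10% dropout), and any serious event between consent and first dose, fall outside the protocol's AE and SAE definitions. Other sections imply an earlier start, so the text is inconsistent and staff have no clear rule. The share of draws follows from the documents; the number of events does not, because it rests wholly on an assumed complication rate. The conclusion also assumes that the enrollment visit runs in the order written. The consequence is incomplete reporting of procedural safety. The primary comparison of AEs between arms is not biased. This should be changed because the correction is cheap and bears on what the oversight bodies are told, but it does not threaten the trial's main result.

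**What to change.** 1. In Definition of Adverse Event and Reporting Period and Parameter, record AEs and SAEs related to study procedures from signed consent. Reconcile this with the baseline rule, Table 4 and Clinical information so that all give the same start.
2. In Causality of Adverse Event, add a second attribution beside the product one: related to a study procedure, yes or no. Carry it onto the AE form if it is not already there.
3. List procedure-related events separately, by draw (enrollment and day 15), in all randomised children, including any who were never dosed. Give this listing to the DSMB.
4. Keep first dose as the start for the Fisher comparison. A further Fisher analysis excluding procedure-related events would add little with 33 children per arm and is not needed.

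This changes recording only; it alters no dose, visit or clinical rule. The staff who would notice these events are already at the visit. The cost is revised wording, at most one form field, a few more completed forms and possibly an additional SAE report.
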